3. STUDY DESIGN

Study design: Single-center, single-blind, randomized controlled trial

Primary outcome:

1. Change in the average daily GERD symptom severity score from baseline to the last week of the study in the expanded vs. standard group. GERD symptom severity is based on the sum of scores assessing the severity of daytime heartburn, nighttime heartburn, and acid reflux each on a 0-4 point scale (none, mild, moderate, severe, very severe; higher scores signify worse symptoms).

Secondary outcomes:

1. Ratio of the sum of positive correlations over the sum of negative correlations in GSR (or HRV) across patient-provider encounters for standard vs. expanded visit types and for responders vs. non-responders (those with a 50% or greater improvement in their GERD symptom severity).
2. Absolute change in GSR (or high frequency HRV signal) in patient recordings from the beginning of the study visit to the end of the study visit and correlation with subsequent change in GERD symptom severity.
3. Differences in blinded ratings of 2 minute thin slices of study visit videos from the beginning to the end of the study in supportive global impressions (e.g., engagement, relaxed, patient seems pleased/satisfied) and non-verbal behaviors (e.g., smiling) between standard and expanded visit types and correlation with subsequent change in GERD symptom severity.

Study population:

Men and women age 24-70 with heartburn symptoms 3 or more days per week not responsive to proton pump inhibitors or with known functional heartburn. We will enroll until we reach 60 completing subjects.

Study location:

University of California Davis Medical Center

Length of subject participation: 8 weeks

Length of study enrollment: 2 years

Groups:

- 1) Standard visit (n=30), modeled after an empathic, high quality conventional primary care visit.
- 2) Expanded visit (n=30), modeled after a visit with an integrative medicine provider

Randomization:

The randomization code will be generated by the study statistician as described below (sections 4.3 and 9.2). The study will be single-blinded (study providers and the research team will know what the subject is receiving but the subject will not). Randomization will be stratified based on study provider. We anticipate 5 or 6 providers each seeing 10-12 subjects (5-6 standard visits, 5-6 expanded visits).

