9. STATISTICAL CONSIDERATIONS

9.1 General Design Issues

Design: This is a single-blinded randomized controlled trial in which subjects will be randomized in a 1:1 fashion to receive either an expanded or standard visit with a healthcare provider about their GERD symptoms and then treated with amitriptyline or omeprazole for 8 weeks to determine whether an expanded visit can augment the effects of a medication compared to a standard visit.

Primary hypotheses:

1. Subjects who receive an expanded visit will have a greater improvement in their GERD symptoms after 8 weeks of treatment with amitriptyline or omeprazole compared to subjects who receive a standard visit.

Secondary hypothesis:

1. Patient-provider dyads in expanded visits will have a greater percentage of the total visit time spent in physiologic concordance (measured by either GSR or HRV) compared patient-provider dyads in standard visits.
2. Percentage of visit time with physiologic concordance (in GSR or HRV) will be correlated with GERD symptom improvement.
3. Subjects who experience physiologic changes similar to those elicited by mind-body techniques (i.e., decreased GSR and increased high frequency HRV) over the course of their visit (first several minutes compared to the last several minutes of the visit) will demonstrate greater improvements in GERD symptom severity than subjects who do not.

4. Healthcare providers in expanded visits will demonstrate more patient-centered non-verbal behaviors (e.g., smiles and gazes) and global impression (e.g., engaged, friendly, relaxed) compared to providers in standard visits as rated by blinded reviews of thin slices of video excerpts.
5. Patient and provider smiling at the end of study visits will be significantly associated with GERD symptom improvement 8 weeks later.

Primary outcome:

1. Change in the average daily GERD symptom severity score from baseline to the last week of the study in the expanded vs. standard group. GERD symptom severity is based on the sum of scores assessing the severity of daytime heartburn, nighttime heartburn, and acid reflux each on a 0-4 point scale (none, mild, moderate, severe, very severe; higher scores signify worse symptoms).

Secondary outcomes:

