9.2 Sample Size and Randomization

The combined standard deviation (root mean square error) in my pilot fellowship study was 1.5⁶⁴. We are conservatively assuming that this number will likely be larger in this study given the greater number of providers involved. Given 30 subjects in each group (n=60 total), 80% power, a two-sided significance test with alpha = 0.05, the minimal detectable difference (MDD) in GERD symptom severity scores between the standard and expanded groups given the estimated standard deviations (SD) is shown in the adjacent table. These MDD values are similar to those found in my fellowship study⁶⁴ and are clinically meaningful^{86,87}.

Minimal Detectable Difference Between Groups	
SD	MDD
1.5	1.10
2.0	1.47
2.5	1.84

Treatment Assignment Procedures

A randomization scheme will be devised before the start of the study by the study biostatistician who will retain the code and will be responsible for breaking the blind at the end of the study. We do not anticipate a need to break the blind during the study because we are not expecting serious adverse events to occur more frequently in one visit group than another. Randomization will be stratified by provider, with permuted block sizes of 2 and 4 with a goal to have 5-6 providers each see 10-12 subjects. If a provider cannot commit to this many visits, the study biostatistician may need to adjust the randomization scheme and we will consent additional providers.

The study biostatistician will enter the randomization scheme into REDCap and subjects will be randomized immediately prior to the study visit intervention.

If a subject drops out or is unable to complete the study, the statistician may need to rebalance the randomization scheme.

Subjects will be informed of their visit group assignment during the debriefing at the end of the second study visit.

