9.5.2 Secondary Outcomes

1. To analyze physiologic synchrony in GSR, first, an average slope of the GSR will be calculated in the patient and provider recordings in moving 5 second windows, offset by 1 second. Next, Pearson correlations with lag zero will be calculated over successive 15 second windows between time-locked patient and provider GSR slope values. Then, a single session index will be calculated from the ratio of the sum of the positive correlations across the entire visit divided by the sum of the absolute value of the negative correlations across the entire visit. To reduce skew, the natural logarithm of the index will be calculated. Thus, an index value of zero reflects equal positive and negative correlations, a value greater than zero reflects more concordance in GSR than not, while a value less than zero reflects less concordance in the dyad (less than 50%)⁸². These index values will be used in GLM analyses with GERD symptom severity and/or correlated with visit type.

We will also perform similar analyses on the HRV data – comparing variation in the beat-to-beat intervals over short segments of time and calculating Pearson correlation coefficients for time-locked patient and provider data for these intervals.

2. We will calculate absolute changes in both GSR and also high frequency HRV within study subjects from the beginning to the end of the study visit. We will assess the Pearson correlation between these changes and reported changes in GERD symptom severity. We will also look at absolute levels of GSR and HRV at the end of the study visit and compare those values with changes in GERD symptom severity in GLM models. As an exploratory analysis, I will test whether changes in GSR and HRV are a function of baseline perceived stress and if that relationship differs between the standard and expanded visit interventions.
3. To analyze study visit videos, 2 minute thin slices of each video at three time points (beginning, middle, and end of study visits) will be analyzed by trained and blinded coders, for the presence of 1) micro-level non-verbal supportive behaviors (e.g., gazes, smiles, nods, gestures – measured as absolute number or

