length of time) as well as 2) macro-level impression ratings of the interaction (e.g., engagement, friendliness, relaxed, empathic, reciprocity – measured on a 1-9 scale). The PI will meet weekly with the coders to review findings and resolve areas of disagreement until greater than 70% concordance is achieved between coders using Cronbach's alpha. Each of these variables will be assessed in a GLM examining time, visit type, and time x visit type effects. We will also calculate the Pearson correlation coefficient for each variable relative to improvement in GERD symptoms and construct a GLM examining patient and provider smiling as a predictor of improvement in GERD symptoms. Other models may also be constructed based on the results of the initial video analyses.

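### The marker-to-symptom tests in 9.5.2 treat about 60 dyads from 5-6 providers as independent; they should be adjusted for provider and for visit type

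*Combined protocol and SAP*

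**What the plan says.** Section 9.1 states two hypotheses that link what happens in a visit to later symptoms. Hypothesis 2: "Percentage of visit time with physiologic concordance (in GSR or HRV) will be correlated with GERD symptom improvement". Hypothesis 5: "Patient and provider smiling at the end of study visits will be significantly associated with GERD symptom improvement 8 weeks later". Hypothesis 3 makes a similar claim for the patient's own change in GSR and high-frequency HRV.

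The planned tests are in 9.5.2:
- Video variables: "We will also calculate the Pearson correlation coefficient for each variable relative to improvement in GERD symptoms", plus a GLM with patient and provider smiling as predictors.
- Concordance index: "These index values will be used in GLM analyses with GERD symptom severity and/or correlated with visit type". No covariates are named.
- Patient GSR/HRV change: a Pearson correlation with symptom change.

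The overall method list in 9.5 is descriptive statistics, Pearson correlations and general linear models such as ANCOVA. No mixed model or clustering method appears in 9.5 or 9.6. Provider enters only as the randomisation stratum, "with a goal to have 5-6 providers each see 10-12 subjects"; provider gender is an exploratory moderator in 9.5.1. On the outcome SD, 9.2 says: "We are conservatively assuming that this number will likely be larger in this study given the greater number of providers involved".

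**The concern.** A pooled Pearson test, or a one-predictor GLM without provider (the same test), refers its statistic to the distribution for 60 independent pairs. Here the pairs come in 5-6 groups. Provider smiles, gaze and nods, and the provider's half of every concordance value, are measured repeatedly on the same few people, so a provider component in the marker is plausible. The plan's remark on the SD allows for one in the outcome too.

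With so few providers, a chance alignment between provider style and provider mean outcome can look like a marker-symptom link. In the other direction, provider spread in the marker can dilute a real link within providers. Stratified randomisation protects the visit-type comparison but not these associations, because concordance and smiling are not randomised.

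The associations are the evidence for the secondary aims on physiologic markers and on patient and physician behaviors. One or two unusual providers could create or hide an apparent mechanism.

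**Working it through.** **The plan's own figure.** The only power statement is for the primary outcome: "Given 30 subjects in each group (n=60 total), 80% power, a two-sided significance test with alpha = 0.05". A two-sample t-test with 58 df (noncentral t) gives minimal detectable differences of 1.103, 1.471 and 1.839 at SD 1.5, 2.0 and 2.5. The plan's 1.10, 1.47 and 1.84 are reproduced. No figure is given for the marker-to-symptom tests.

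**Inputs from the documents.** 60 completing subjects (section 3); 5-6 providers with 10-12 subjects each (9.2), run as 5 x 12 and 6 x 10; two-sided alpha 0.05, carried over from the primary outcome.

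**Assumptions.** The documents give no ICCs and no target correlation. Marker ICC is varied from 0 to 0.5, outcome ICC from 0 to 0.44, and the dyad-level correlation is 0.35 for power. The value 0.44 follows if SD 2.0 applies and all of the rise from 1.5 is between providers: (4.00 - 2.25)/4.00 = 0.4375. It is an upper bound for that SD.

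**Approximation.** With m visits per provider and independent provider effects in marker and outcome, the variance of r is inflated by about 1 + (m - 1) x ICC_marker x ICC_outcome. For m = 12 and 0.5/0.1 this is 1 + 11 x 0.05 = 1.55. The type I error is then 2 x (1 - Phi(1.96/sqrt(1.55))) = 11.5%. At 0.1/0.1 the factor is 1.11 and the error 6.3%. If either ICC is 0 there is no inflation.

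**Simulation.** 40,000 trials per setting. The pooled Pearson test (58 df) is compared with the correlation within provider (54 df for 5 x 12, 53 df for 6 x 10). The power columns assume no link between provider means.

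| Marker / outcome ICC | Pooled type I, 5 x 12 | Pooled type I, 6 x 10 | Power pooled, 5 x 12 | Power within provider, 5 x 12 |
|---|---|---|---|---|
| 0 / 0 | 4.9% | 5.1% | 79% | 76% |
| 0.1 / 0.1 | 6.1% | 6.0% | 71% | 76% |
| 0.3 / 0.05 | 6.5% | 6.2% | 64% | 76% |
| 0.3 / 0.1 | 8.1% | 7.4% | 62% | 76% |
| 0.5 / 0.1 | 10.3% | 9.3% | 52% | 77% |
| 0.5 / 0.44 | 26.5% | 23.9% | 48% | 77% |

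The within-provider test has a type I error of 4.8-5.3% in every setting. A repeat run gave 26.2% in place of 26.5%.

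**If the link also holds between providers.** With r = 0.35 at both levels (6 x 10), pooled against within-provider power is 74% vs 76% at 0.3/0.05, and 79% vs 76% at 0.1/0.05.

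**Visit type.** The trial hypothesises that expanded visits raise both improvement (primary) and the markers (secondary 1 and 4). Take an outcome effect of 1.103/1.5 = 0.735 SD and assume the same for the marker, with no dyad-level link and no provider variance. Each variable gains variance 0.735^2/4 = 0.135, so the induced correlation is 0.135/1.135 = 0.119. The pooled test then rejects about 15% of the time. At ICCs 0.3/0.05 the pooled test rejects 17% and the test adjusted for provider alone 20%, because removing provider variance sharpens the correlation induced by visit type. With provider and visit type both in the model the rate is 5%.

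**Cost.** With no provider variance, adding provider and visit type lowers power at r = 0.35 from 79.6% to 75.9% (5 x 12) and from 79.4% to 74.8% (6 x 10).

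**The case against.** The strongest reply is that the size is unknown. Inflation needs provider variance in both variables, and the documents quantify neither. Several features should limit it: the visits are scripted with identical advice, providers are told to keep empathy equal (5.1), recordings are reviewed for fidelity (5.1, 9.4), and the outcome is a patient diary eight weeks later. Extra providers may be consented (9.2), which would make the groups smaller. This stands: with both ICCs at 0.1 or below, the error is 5-6%.

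A reader might infer from the SD table that the plan expects an outcome ICC of 0.44, and so an error near 26%. It does not. Section 9.2 tabulates 1.5, 2.0 and 2.5 as a cautious range and does not forecast 2.0 or assign the whole increase to providers.

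A reader might also infer that pooling always loses power. It does not if the same link holds between providers.

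A further objection is that hypotheses 2 and 5 do not condition on provider, so differences between providers are part of the question. That is a fair reading of the wording, but 5-6 providers cannot support a test of it.

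Lastly, adjusting for provider alone is not enough, as the visit-type calculation shows. That objection is right and is built into the fix.

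**Conclusion.** The concern holds in a limited form. The stated marker-to-symptom tests ignore provider, and where marker and outcome both vary between providers their nominal 5% level is not kept: about 6% at assumed ICCs 0.1/0.1, 8% at 0.3/0.1 and 10% at 0.5/0.1, with 26% only at an upper-bound outcome ICC. The power loss, about 12 points at 0.3/0.05 (64% vs 76%), depends on there being no matching link between providers.

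Hypothesis 5 and the concordance index of hypothesis 2 are most exposed, because the provider supplies part of the marker. For hypothesis 2 the planned test is a GLM with unstated covariates, not a Pearson test; the point applies as long as provider is not among them. A purely patient-level marker, as in hypothesis 3, keeps about 5% with respect to provider.

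Two stronger readings are not supported. The point does not reach the primary comparison or its detectable differences, since visit type is randomised within provider. Nor do the documents show that case mix differs between providers; 6.2.3 says only that subjects see the provider they are scheduled with that day.

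The change is worth making because the ICCs cannot be known beforehand and the adjusted test is valid whatever they are.

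**What to change.** In 9.5.2, base each test of a marker-symptom association on a GLM of follow-up symptom severity, adjusted for baseline severity as in the primary ANCOVA, with the marker as predictor and provider (fixed factor, 5-6 levels) and visit type as covariates. The partial correlation given these terms is equivalent. State that a negative marker coefficient means more improvement. Report the pooled Pearson correlation as description, without a p-value.

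No new data are needed, since provider and visit type are already recorded for randomisation. Provider takes 4-5 df and visit type 1, so 5-6 df in all, or about 4-5 points of power if providers do not differ. The adjusted test addresses the association within provider and visit type. Associations that exist only between providers, or only through visit type, are left to description, and the plan should say so.

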9.6 Data Analyses

We will perform descriptive statistics on the sample demographics similar to our prior paper⁶⁴ including age, gender, race, ethnicity, body mass index (BMI), smoking status, and current medication use for GERD symptoms. We will also assess whether perceived stress, perceived empathy (both patient and provider), personality type (five factor inventory), or demographic factors modify improvement in GERD symptoms using generalized linear models. We will use the GERD-HRQL, NIH PROMIS GERD, and GSRS as adjunct/corroborating measures of GERD symptom severity. Blood samples will be processed and stored at - 80°C for later omics-based analyses that will be the subject of a future grant/study.

10. DATA COLLECTION AND QUALITY ASSURANCE

10.1 Data Collection Forms

Most questionnaire data will be collected on iPads at the study site using Research Electronic Data Capture (REDCap; <http://project-redcap.org/>) forms. In the event that a subject cannot physically return for the second study visit, a link to the follow-up questionnaires will be emailed to the subject. Subjects will complete GERD symptom dairies either online (REDCap) or in paper format daily. Paper data will be doubled entered into a REDCap database by study personal and checked for consistency. REDCap is a secure, web-based application developed at Vanderbilt University for electronic collection and management of clinical research study data and is hosted locally by UC Davis.

Study staff will maintain an electronic screening file and enrollment log file and paper files of consent forms.

Study participant confidentiality will be maintained by a unique identifier. An electronic file linking participants' personally identifying information and study ID will be password protected. All paper data will be stored in a locked filing cabinet. Only study affiliated personnel will have access to the study database and associated files. Electronic communication with collaborators will only involve deidentified information. All published data will be presented in aggregate format and deidentified.

10.2 Data Management

All paper symptom diaries will be reviewed in real time with subjects to ensure that data can be transferred completely and accurately to electronic form. Such data will be double entered and cross checked as described above. All data (questionnaire, physiologic, video) will be cleaned by study staff and reviewed every 1-2 months by the study PI to ensure accuracy, completeness, and timeliness of subsequent analyses.

10.3 Quality Assurance

10.3.1 Training

The study PI will personally train and supervise all research coordinators and interns working on the study in collaboration with relevant consultants to ensure that study measures are collected appropriately. All research coordinators/interns will have completed the appropriate human subjects training programs and may complete additional training depending upon the capacity in which they will serve in the study.

10.3.2 Protocol Deviations

Protocol deviations will be documented and reported to the UC Davis IRB. Unapproved major protocol deviations will be reported to the IRB and NCCIH within 5 business days of discovery.

Unapproved minor protocol deviations will be reported to the IRB at the time of the annual continuing review and to NCCIH annually as well. Should a protocol deviation become repetitive and/or problematic, the investigational team may consider submitting a protocol amendment to adjust study procedures.

10.3.3 Monitoring

The study PI will regularly review study questionnaires, HRV and GSR data, video recordings, and logs for completeness and quality. Such review will follow each subject initially but will occur at least every 1-2 months for the duration of the study.

11. PARTICIPANT RIGHTS AND CONFIDENTIALITY

11.1 Institutional Review Board (IRB) Review

This protocol and the informed consent documents and any subsequent modifications will be reviewed and approved by the UC Davis IRB.

11.2 Informed Consent Forms

Written informed consent will be obtained by a study team physician at the initial study visit after reviewing inclusion and exclusion criteria, the participant's symptom diary, and the electronic medical record if the participant is a patient at UC Davis. The consent form will describe the purpose of the study, the procedures to be followed, and the risks and benefits of participation. Participants will have the opportunity to ask questions. A copy will be given to each participant and this fact will be documented in the participant's record. Participants who cannot consent for themselves or who are not fluent in English will not be eligible to participate due to the nature of the study.

11.3 Participant Confidentiality

Study visits will be conducted in a private setting. Whenever possible, questionnaire data will be collected electronically using REDCap. REDCap is a secure, web-based application developed by Vanderbilt University for electronic collection and management of clinical research study data. All electronic data not gathered using REDCap (symptoms diaries, physiologic data, video recordings) will be stored on a UC Davis shared drive which is backed up regularly to protect against data loss and is behind the UC Davis firewall. Any data that cannot be collected directly onto a shared drive (i.e., must be saved on a local hard disk during data collection) will be collected on an encrypted laptop and transferred to a UC Davis-affiliated server shortly after collection. Any paper questionnaire data will be stored in a locked filing cabinet.

Only those researchers involved in the study will have access to electronic and paper data. The file linking participants' personally identifiable information with their participant identification number (PID) will be password protected and access will be restricted to the fewest number of staff required but will include at least the PI and a research coordinator. Electronic access to videos will also be password protected. All paper records will be kept in a locked file cabinet. All computer entry and analysis will be done using PIDs only. Any data, forms, reports, video recordings, and other records that leave the site will be identified only by a PID to maintain confidentiality. Digital video files may be stored for up to 12 years but may be destroyed sooner.

Information will not be released without written permission of the participant, except as necessary for monitoring by IRB, the NCCIH, and the OHRP.

